6.8 Vital Signs

Collected vital signs will include pulse rate, blood pressure, and temperature.

Results for each vital sign parameter will be listed by treatment group, subject, and time point. Actual values and changes from baseline will be summarized for each time point by treatment groups.

6.9 Post-void residual (PVR) urine volume

PVR urine volume will be summarized descriptively for each treatment by visit. Change from baseline in PVR urine volume will be summarized.

6.10 Other Safety Analyses

6.10.1 Physical Examination

Physical examination results will be listed by treatment group, subject, and time point.

7 Primary Analysis

A primary analysis will occur when all patients have completed 12 weeks following double-blind period or early terminated. Only tables will be produced (no patient listings will be

produced), thus maintaining patient and site/investigator treatment blinding. The primary analysis (topline data) will be a subset of the final analyses performed for the final CSR. Analyses included in the primary analysis will be flagged in the table, figure, and listing mocks.

The main purpose of the primary analysis is for presentation of the key data as soon as possible at an international urological or urogynecological conference to ensure dissemination of results in a timely manner. The topline primary analysis data will include key efficacy and safety analysis from the first 12 weeks after double-blind treatment.

For the purpose of the primary analysis, statistics and programming staff from the vendor CRO, will have blinded and unblinded teams set up for the analysis, per details contained in the SAP and/or other documentation listing those who will be unblinded. Unblinded statistical team will work in a restricted secure study location. Responsibilities of each team are listed in Section 7.1 and 7.2.

Only Allergan study team members and corresponding co-authors will receive the topline primary analysis data (no analysis datasets and listings will be distributed, therefore the Allergan team and co-authors will not be unblinded to patient level data). Those who will be unblinded in Allergan will be listed in another document. No CSR will be authored following the primary analysis.

Full unblinding will occur following the final database lock at the end of the study, for the final CSR.

7.1 ██████████ **Blinded Statistical Team**

The responsibilities of the blinded statistical team are as follows:

- Compile, generate, and review of all blinded TFLs and other reports as required by the primary analysis.
- Secure provision of codes for blinded tables and listings to the unblinded statistical team, who will provide unblinded tables and listings to Allergan unblinded statistician.

7.2 ██████████ **Unblinded Statistical Team**

The responsibilities of the unblinded statistical team are as follows:

- Compile, generate, and review all unblinded TFLs as required by the primary analysis
- Distribute all appropriate primary analysis materials to Allergan statistician via the secure email as password protected zip files.

8 Changes from Protocol-Specified Analyses

No change from protocol-specified analysis.

9 Reference

10 Amendment(s)

Version Number/ Date	Comments	Rationale
2.0 / 07Mar2019	
1. Updated typo to specify that efficacy output uses the mITT population instead of ITT population.2. Updated to remove 97.5% confidence intervals for the primary analysis of primary efficacy variables.3. Specified that CIC must be of duration greater than 1 day to be included in summary tables.4. Updated a typo where “IA” was used instead of “primary analysis”5. Other cosmetic updates	
1. Protocol amendment 1 (finalized prior to the primary analysis) specified to use mITT population for all efficacy analyses. SAP 1.0 has a typo specifying efficacy analyses will use the ITT population. This was changed to mITT to be consistent with protocol amendment 1.2. Protocol amendment 1 only specifies that a 95% confidence interval will be provided for the primary analysis of efficacy variables. SAP 1.0 included a 97.5% confidence interval that was not included in protocol amendment 1, so this was removed.3. The CIC duration was updated, so the CIC summaries will be consistent with the analysis performed in Phase III trials used for drug labeling.4. There was no interim analysis on this study. Using “IA” was a typo and should have referred to the primary analysis.5. Cosmetic updates include the following: section references that were incorrect were fixed, a sentence that was not capitalized was corrected, and text was made subscript where appropriate.

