Both pivotal phase III studies, 191622-095 and 191622-520, achieved a statistically significant and clinically relevant treatment effect of BOTOX 100 U, and results were consistent between the 2 studies. The co-primary efficacy endpoints were met in both studies ( $p < 0.001$ ), with clinically meaningful reductions from baseline in urinary incontinence and clear patient perception of improvement in their condition using the TBS. Furthermore, all secondary endpoints were met in both studies, which included OAB symptoms and HRQOL parameters. Specifically, BOTOX 100 U attenuated all OAB symptoms; thus a significant treatment effect was observed for urinary incontinence, micturition frequency, urgency, and nocturia. The improved ability of the bladder to store urine was reflected in significant increases in volume voided per micturition. Similarly, the secondary endpoints of change from baseline in the Incontinence Quality of Life total summary score and the change from baseline in the 2 multi-item King’s Health Questionnaire (KHQ) domain scores ‘Role Limitations’ and ‘Social Limitations’ at Week 12 were also met ( $p < 0.001$ ).

In terms of safety, adverse events that were higher following BOTOX treatment compared to placebo were primarily limited to local adverse events related to the urinary tract, in particular UTI, bacteriuria, dysuria, and urinary retention. A dose-dependent increase in PVR urine volume was observed post treatment, and a proportion of those patients initiated CIC. However, the proportion of patients with a change from baseline PVR urine volume  $\geq 200$  mL at any time during treatment was low (less than 9% in both studies), and correspondingly, the proportion of patients who initiated CIC was also low (6.5%).

Patients who were enrolled in the pivotal phase III studies had the opportunity of enrolling into a long-term follow-up study, 191622-096. This study has been completed (N=839), and patients will participate in the follow-up study for up to an additional 3 years and receive only active treatment (on fulfillment of Qualification and Day of Treatment Criteria). The final analysis of this extension study demonstrated a consistent efficacy and safety profile over repeated BOTOX treatments.

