## 2.2 Clinical Hypotheses

BOTOX 100 U is more effective compared to placebo, when injected into the bladder using the alternative paradigm (2 trigonal and 8 peri-trigonal injections), in reducing the number of daily urinary incontinence episodes from baseline at Week 12.

BOTOX 100 U has an acceptable/better safety profile, including the risk of incomplete bladder emptying and need for clean intermittent catheterization (CIC), when administered as 10 injections into the lower part of the bladder (2 trigonal and 8 peri-trigonal) of patients with OAB with urinary incontinence.

BOTOX 100U administered into 10 injection sites limited to the lower portion of the bladder (alternative paradigm) rather than 20 sites in the posterior wall is effective in achieving efficacy in patients with OAB while reducing the risk of incomplete bladder emptying in those patients.

BOTOX 100 U, administered using an alternative injection paradigm, is effective for longer duration than placebo as assessed by the difference between treatment groups in the time to qualification for second treatment (qualification for Treatment 2 criteria provided in [Section 5.10.1](#) Request/Qualification for Treatment 2) during the 30 weeks of follow-up after the first treatment injection.

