### **6.3.6.1 Post-void Residual Urine Volume < 200 mL**

No protocol-required action needs to be taken. The patient continues to be reviewed as per the schedule of visits and procedures. CIC may be initiated only if the investigator deems it necessary for patient safety and will be recorded as a clinical decision.

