#### **6.3.7.1 Initiation of Clean Intermittent Catheterization**

As described above in the PVR urine volume section, CIC should be initiated per protocol when one of the following criteria is fulfilled:

- PVR urine volume is  $\geq 350$  mL at any post treatment visit, regardless of whether the patient reports associated symptoms
- PVR urine volume is  $\geq 200$  mL and  $< 350$  mL and the patient spontaneously reports associated symptoms (ie, voiding difficulties, sensation of bladder fullness) that in the opinion of the investigator require CIC

The following will occur when initiating CIC (for elevated PVR urine volume as described above):

- 1) CIC is implemented and the patient should be instructed to perform CIC using sterile, single-use catheters (which will be provided to the patient)
- 2) an adverse event of urinary retention is recorded
- 3) central laboratory urine analysis and culture/sensitivity are performed as per routine requirements at each study visit excluding the clinic visit at Week 24.

- 4) the patient will be seen for a follow-up visit 1 week later where the PVR urine volume, associated symptoms, central laboratory urine analysis and culture/sensitivity will be reassessed. The investigator will determine whether the patient can then be followed per protocol scheduled study visits or whether additional follow-up visits should occur.

Once CIC is initiated, the status of CIC use should be documented in the patient record at each visit (ie, use/non-use). Start date of CIC should be documented, also.

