### **7.3.4 Safety Analyses**

All safety analyses will be conducted on the safety population.

Descriptive statistics will be used to summarize safety endpoints which include adverse events, clinical laboratory (urine analysis), vital signs, PVR urine volume, physical examination, CIC use, concurrent procedures, and concomitant medications.

Adverse events will be coded using Medical Dictionary for Regulatory Activities (MedDRA, Version 19.0 or later). Adverse events will be summarized by primary system organ class and preferred term for each treatment. This summary will include all treatment-emergent adverse events (TEAEs) recorded from first dose of study treatment up to the post-treatment follow-up. Tables of fatal adverse events, SAEs, and adverse events leading to study discontinuation will be summarized by treatment. TEAEs by severity and relationship to study drug will be summarized by treatment.

Parameters for urine analysis will be summarized descriptively by treatment at each visit during the study. Shift tables will be provided for selected laboratory parameters.

Vital signs and PVR urine volume, will be summarized descriptively for each treatment by visit. Change from baseline in PVR urine volume (continuous variable) will also be performed.

Concurrent procedures and concomitant medications will be summarized descriptively for each treatment.

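### SAP version 2.0 counts clean intermittent catheterization (CIC) in summary tables only if it lasted more than 1 day; this narrows the protocol's CIC summary and SAP section 8 does not declare it

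*SAP*

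**What the plan says.** Protocol section 7.3.4 lists the safety items to be summarised descriptively. They include "vital signs, PVR urine volume, physical examination, CIC use, concurrent procedures, and concomitant medications". No minimum duration is attached to CIC.

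Protocol section 2.2 frames the safety hypothesis for the new injection pattern as "including the risk of incomplete bladder emptying and need for clean intermittent catheterization (CIC"). Section 1 describes the Phase III experience in these words: "the proportion of patients who initiated CIC was also low (6.5" per cent). It gives no duration for those episodes.

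The amendment table in SAP section 10, version 2.0, item 3, adds the rule: "Specified that CIC must be of duration greater than 1 day to be included in summary tables". Its rationale is a change made "so the CIC summaries will be consistent with the analysis performed in Phase III trials used for drug labeling". SAP section 8 states: "No change from protocol-specified analysis".

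Two protocol passages bear on where short CIC would otherwise be seen. Under section 6.3.7.1, when CIC is started for a raised post-void residual (PVR) volume, "an adverse event of urinary retention is recorded", whatever the later duration. Under section 6.3.6.1, at a PVR below 200 mL, "CIC may be initiated only if the investigator deems it necessary for patient safety and will be recorded as a clinical decision".

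**The concern.** A patient catheterised for one day or less did start CIC, and so falls within an unqualified summary of CIC use and within the hypothesis about the need for CIC. Under version 2.0 that patient is not counted in the CIC summary tables the rule governs. The protocol sets no such limit, and the SAP section meant to list departures from the protocol records none.

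Few patients are expected to use CIC, so one patient more or less changes the reported percentage visibly. The outcome is also one that the alternative injection pattern is hoped to improve. A reader of the results should be able to see both how many patients started CIC and how many continued beyond a day.

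**Working it through.** **1. Direction.** Patients counted = patients with any CIC − patients whose CIC lasted 1 day or less. The subtracted term is zero or positive, so the rule can only lower the count or leave it unchanged.

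**2. Whether short episodes can occur.** Protocol section 6.3.7.2 lets CIC stop at any time once its criteria are met, without waiting for a scheduled visit. Episodes of 1 day or less are therefore possible. Neither document says how common they are.

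**3. Number of BOTOX patients.** The plan needs 102 patients at Week 12 and allows 10% dropout: 102 / (1 − 0.10) = 113.3, rounded up to 114, which reproduces the protocol's figure. With 2:1 allocation, 114 × 2/3 = 76 BOTOX patients. I assume all 76 are treated and so enter the Safety Population.

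**4. Illustrative size.** The plan states no expected CIC count. Take 6.5% (Protocol section 1) as an any-duration rate for BOTOX 100 U, which is an assumption: 76 × 0.065 = 4.94 expected users. Let q be the share of users whose CIC lasted 1 day or less, also assumed. Counted = 4.94 × (1 − q); omitted = 4.94 × q; reported rate = 6.5% × (1 − q).

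| Assumed q | Counted | Omitted | Reported rate |
|---|---|---|---|
| 0 | 4.94 | 0 | 6.5% |
| 10% | 4.45 | 0.49 | 5.9% |
| 25% | 3.71 | 1.24 | 4.9% |
| 50% | 2.47 | 2.47 | 3.3% |

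If the 6.5% already excludes short CIC, the table subtracts it twice and does not apply.

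**5. What one patient is worth.** 1/76 = 1.3 percentage points. Observed rates and exact 95% intervals are 5/76 = 6.6% (2.2% to 14.7%), 4/76 = 5.3% (1.5% to 12.9%) and 3/76 = 3.9% (0.8% to 11.1%). A shift of one or two patients alters the printed rate but is small against the sampling uncertainty.

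**6. Where short CIC would still appear.**

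| Route to CIC | Retention adverse event table (SAP 6.5, 6.5.1) | Concomitant procedures (SAP 6.3) |
|---|---|---|
| PVR 350 mL or more, or 200 to below 350 mL with symptoms requiring CIC | Yes, whatever the CIC duration | Yes |
| PVR below 200 mL, investigator's decision | No, definition not met | Yes |

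The retention table misses the second route. SAP section 6.3 says that catheterization is listed with its reason and that procedures are summarised by an unspecified layout; it does not say that the summary isolates CIC. The topline analysis produces tables without listings (Protocol section 7.6, SAP section 7), so a listing could not fill the gap there.

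**The case against.** The strongest defence is comparability. The trial has no arm treated with the standard injection pattern, so whether the new pattern lowers CIC risk can only be judged against historical data. If the Phase III labelling analysis counted only CIC over 1 day, the same rule is needed for a like-for-like comparison, and an any-duration count set against it would be unfair to the new pattern. This stands as a reason to keep the row for CIC over 1 day. It does not justify showing that row alone: the comparison with placebo inside the trial needs no historical definition, and the protocol describes the 6.5% only as patients who initiated CIC. Whether that figure used the rule rests on the amendment rationale alone.

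Second, the protocol never defines a countable case of CIC and leaves variable definitions to the SAP, so setting a threshold could be called a definition and not a departure. That is arguable, but a threshold on an item the protocol leaves unqualified is worth declaring either way.

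Third, most short CIC is captured elsewhere, as step 6 shows. That is true and limits the harm. A mismatch between the retention and CIC tables is also not peculiar to this rule, since the protocol already permits CIC without a retention event.

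Fourth, the readable SAP passes from section 6.3 to 6.5, and the rule is seen only in the amendment table. A fuller CIC section may exist, so I do not claim that short CIC is removed from every table or that an any-duration row is absent.

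**Conclusion.** The point holds as a matter of reporting and declaration. The current SAP restricts CIC summaries to episodes over 1 day, the protocol's plan has no such limit, and SAP section 8 does not mention it. Any effect is in one direction. Its size is unknown and may be zero; under the assumptions in step 4 it is 0 to about 2.5 of some 5 BOTOX patients.

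Several stronger readings are tempting and are not supported:

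- That CIC is the trial's main safety outcome. It is named in the hypotheses, but it is one of several descriptive safety items, and SAP section 6 plans no inferential safety comparison.
- That CIC is in fact undercounted. No document shows that any episode lasted 1 day or less.
- That the loss falls mainly on the BOTOX arm. The protocol reports more retention after BOTOX than after placebo, which makes this plausible, but nothing is said about short episodes by arm.
- That the rule was adopted after results were seen. Version 2.0 is dated 07Mar2019, and the documents do not say whether this preceded the topline analysis.

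**What to change.** 1. In the CIC summary, give two rows by treatment group: patients with CIC of any duration, and patients with CIC over 1 day. Label the second as the comparison with Phase III. If the topline tables include CIC, show both rows there too.
2. Record the 1-day rule and its reason in SAP section 8.
3. State which definition produced the 6.5% in Protocol section 1, so that the historical comparison uses the matching row.

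No new data are needed, because the protocol already collects CIC start and stop dates (sections 6.3.4, 6.3.7.1 and 6.3.7.2). The cost is one extra table row and a short SAP entry. The any-duration row may show a slightly less favourable CIC rate.
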